Purpose of the Study – The purpose of this study is to address the key question of whether and how family health history (FHH) is adopted as a tool to more efficiently manage patients at risk for breast, colon, ovarian, and hereditary cancer syndromes as well as thrombophilia and coronary heart disease (CHD) and to provide evidence supporting clinical utility -- improved health behaviors in patients and physician screening recommendations. Five health care delivery organizations will participate in this demonstration project: Duke University, the Medical College of Wisconsin, the Air Force, Essentia Health, and the University of North Texas Health Science Center. The study will take place in 'real world' clinical, socio-cultural, and demographically diverse (rural, underserved, academic, family medicine) clinics (n=34) in 5 states (CA, MN, NC, WI, TX) that include genomic medicine 'early adopter' and 'naïve' sites, as well as those that are EMR-enabled and others that are not, and will use a cluster randomized controlled pragmatic hybrid type III implementation-effectiveness observational study design. We anticipate enrolling **7000 English or Spanish speaking adult participants (at a minimum) over a 3-year period**; to reach this goal we need to enroll ~300 participants from each intervention clinic (assuming 10 of the 34 clinics will be dedicated controls). Specifically we will use Healthcare Effectiveness Data and Information Set (HEDIS) measures as intermediate clinical effectiveness measures for CHD and the selected cancers as well as survey/formative data and electronic medical record (EMR)

data as outcomes measures. The research model is purposely designed to mimic clinical delivery as an important step toward widespread implementation and sustainability. In addition we will use a cost-effectiveness analysis to compare usual care to the FHH guided preventive health model. **The completion of this project will result in an optimal strategy for integration of FHH data collection and clinical decision support (CDS) tools into an EMR and demonstrate the utility of the FHH intervention among diverse primary care patients, their settings, their providers, and the health systems that deliver their care.**

Specific Aim 1: To optimize the collection of patient entered FHH in diverse clinical environments for coronary heart disease, thrombosis, and selected cancers

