Benefits: Two aspects of the study will provide information that will improve patient care in primary care: 1) Enhancing primary care physician decision making by the application of individualized evidence-based algorithms based on patient characteristics and 2) Enhancing patient decision making by using active patient facing tools to promote patient engagement and activation. Overall we anticipate greater patient and provider satisfaction and the potential for streamlined workflows with improved information exchange. Risk stratification with decision support can assist in decision making for both patients and providers by 1) increasing knowledge, 2) lowering uncertainty, 3) reducing the likelihood of indecision, and 4) increasing the match between decisions and values. These effects have both cognitive and emotional components that can influence “decisions” by shifting perceptions of: disease, disease risk, treatment, and treatment benefits. Patients are also given a copy of their pedigree which can be shared with and distributed among family members as well as retained by the patient as documentation of their effort to collect the family history and to share with other clinical providers involved in their care.

Costs to the Subject – There will be no costs to patients or providers for their participation, though it does require a small time commitment.

Data Analysis & Statistical Considerations – Effectiveness data will be summarized with descriptive statistics and plots. Generalized linear ordinal regression models (GLO)(the function `ordgelm` from the R statistics package) will fit ordinal survey outcomes to the continuous outcome variables. Associations will be considered significant when the regression coefficient is not zero; a false discovery rate of 5% will be used to correct

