for multiple comparisons. Multivariate analysis will control for clinic and provider. A p-value of <0.1 in stepwise regression will identify significant factors such as demographics, intent to change, and their interactions. The analyses for the multiple outcomes will follow the same procedure as the survey outcomes but using a logistic regression model that includes the 7 covariate factors (see sample size section). Although the study is implemented at the level of the clinical practice, the likelihood of clustering is low given that all participants undergo the intervention and the intervention is aimed at both the patient and the provider; however, to address the possibility of clustering, we will calculate a design effect; if it is 1 we will use standard tests and generalized linear mixed models with clinic and state as random effects, if not we will adjust the confidence intervals using a conditional logistic regression. Effect size bias is extremely unlikely in this study as all individuals within the clinics are offered the intervention, preventing the imbalance in treatment assignment that can lead to inaccurate point estimates.

ORCA survey data will be analyzed using this validated survey's scoring method. The results will be used to categorize institutions and/or the individual clinics according to their flexibility for adapting to new ideas/technologies, which will then be included as an explanatory variable in the analysis of the effectiveness data captured during the trial as well as to help understand barriers encountered during the implementation process.

Key Informant Interview data analysis will proceed with an initial review of the transcripts conducted independently by study investigators. Each coder will identify major thematic categories included in the *a priori* theoretical model and emergent categories. The coders will work together to develop a revised schema for content coding. Once the schema has been finalized, the coders will code the transcripts for relevant categories and have discussions that may lead to further revision and refinement of the code book. Findings from the pre-implementation interviews will be used to create a tailored implementation plan at each site.

As of 01/20/2017 [name] is no longer on key personnel for this protocol, however she has been added to outside key personnel and will assist with writing study publications. She will see data summaries only, and not individual data.

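### The clustering rule is the wrong way round: the clinic random-effects model is kept for a design effect of 1, and the clustered branch cannot properly test the ORCA category

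*Combined protocol and SAP*

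**What the plan says.** All of the rule stands in Data Analysis & Statistical Considerations.

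- Clustering is expected to be small: "the likelihood of clustering is low given that all participants undergo the intervention".
- A design effect is calculated all the same. The first branch reads: "if it is 1 we will use standard tests and generalized linear mixed models with clinic and state as random effects".
- The second branch covers any other value of the design effect: "if not we will adjust the confidence intervals using a conditional logistic regression". No stratum, ICC, formula or tolerance around 1 is given.
- Separately, and without condition, "Multivariate analysis will control for clinic and provider". Whether by fixed effects, random effects or strata is not said.
- The ORCA survey will be used to "categorize institutions and/or the individual clinics according to their flexibility", a grouping "which will then be included as an explanatory variable in the analysis of the effectiveness data captured during the trial".
- Survey outcomes are handled by ordinal regression models that "will fit ordinal survey outcomes to the continuous outcome variables"; the multiple outcomes follow the same procedure with logistic regression.

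Purpose of the Study gives the scale: "Five health care delivery organizations will participate in this demonstration project", with 34 clinics, 10 of them dedicated controls, and a minimum of 7000 participants.

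**The concern.** A design effect of 1 means that the between-clinic variance is zero. A random-effects model is the standard tool when that variance is not zero, so the two branches look swapped.

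The method given for the clustered case does not fill the gap. Conditional logistic regression removes everything that is constant within a stratum, so the choice of stratum decides what can be estimated, and the stratum is not named. The ORCA category is constant within a clinic, or within an institution, and is the one factor at that level that the analysis section commits to fitting. Depending on how the analyst fills the gap, its main effect is either lost or tested with a standard error that leaves out clinic variation.

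The reason offered for expecting little clustering does not help. Giving everyone the same intervention does not make outcomes independent within a clinic, because patients there still share providers, workflow and local population.

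**Working it through.** **Cluster size.** Purpose of the Study and Selection of Subjects give 34 − 10 = 24 intervention clinics at about 300 each: 24 × 300 = 7200, which agrees with the stated minimum of 7000 to within 3%. Working back, m = 7000/24 = 291.7 per clinic. The documents give no ICC or outcome rate, so the ICC values 0.001, 0.01 and 0.05, an outcome rate of 30% and a two-level ORCA category in 12 v 12 clinics are assumptions.

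**Which branch applies.** Design effect = 1 + (m − 1) × ICC = 1 + 290.7 × (0.001, 0.01, 0.05) = 1.29, 3.91, 15.5. An estimated design effect is essentially never exactly 1, so a tolerance matters. If the ICC estimate is floored at zero and anything above 1 counts, the clustered branch is taken 46%, 77% and over 99.9% of the time at ICC 0, 0.001 and 0.01. If a 5% F test decides, the figures are 5%, 25% and 99.6%.

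**Stratum = clinic.** In the conditional likelihood, a clinic with d events and category x contributes a factor exp(γxd) to the numerator and to every term of the denominator, so γ cancels. A numerical check (24 clinics × 292, one patient-level covariate, simulated ORCA effect 0.4) gives a log-likelihood of −4258.42 at γ = −2, 0, 0.4 and 3. A period-by-ORCA term is estimable in the same data: −4258.42 at 0, −4275.96 at −0.5 and −4292.06 at 0.5.

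**Clinic as fixed effects.** ORCA plus 24 clinic indicators is 25 columns of rank 24, so the main effect is lost again.

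**Stratum = institution.** ORCA set by clinic is estimable (log-likelihood −4400.40 at 0, −4343.17 at 0.4). ORCA set by institution is flat at −4400.40.

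**Wider strata and no clinic term.** True size of a nominal 5% test = 2 × [1 − Φ(1.96/√DE)], where DE is the design effect.

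| ICC (assumed) | DE, m = 291.7 | True size | DE, m = 100 | True size |
|---|---|---|---|---|
| 0.001 | 1.29 | 8.5% | 1.10 | 6.2% |
| 0.01 | 3.91 | 32.1% | 1.99 | 16.5% |
| 0.05 | 15.5 | 61.9% | 5.95 | 42.2% |

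The m = 100 columns allow for smaller analysed numbers. Selection of Subjects removes people with a study disease from the analyses of that disease, and follow-up surveys are requested by email. The value 100 is itself an assumption. Simulation at 292 per clinic with five institution strata (20,000 data sets per ICC) gave 8.5%, 32.3% and 62.2%.

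**The model already named.** A logistic model with a clinic random intercept, tested on 24 − 2 = 22 degrees of freedom, gave 5.9%, 5.4% and 5.3% (2,000 data sets per ICC). State and provider terms were not in that simulation.

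**ORCA set by institution.** With 2 v 3 institutions, clinic ICC 0.01 and institution ICC 0.005 to 0.02, the true size is 19–34% for a clinic-level test on 22 df. It is 13% with institution-level standard errors but still 22 df, and 5.1–5.3% with institution-level standard errors and 5 − 2 = 3 df.

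**Patient-level factors.** With clinic strata, size was 4.9%, 5.0% and 4.8%.

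**Ordinal outcomes.** Standard conditional logistic regression takes a binary outcome, so the clustered branch names no method for the ordinal survey outcomes.

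**The case against.** The best defence is that the large error rates need two things together: strata wider than clinic and no effective clinic term. The plan says without condition that clinic and provider will be controlled, and its clustering sentence starts from implementation at practice level, so clinic is the natural stratum. On that reading nothing is falsely significant; the ORCA main effect simply cannot be estimated. That stands as a limit on the error figures, but not as a rescue. Clinic strata and clinic fixed effects both remove the effect, and clinic random effects are the model that the rule keeps for a design effect of 1.

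The reach is also narrower than a reader might infer. It is tempting to say that the comparison with control clinics is lost. Design & Procedures describes that comparison as one of change in care, and such a contrast varies within clinic and survives clinic strata. It is equally tempting to add clinical setting to the losses. Selection of Subjects mentions differences across settings as a reason to keep enrolling, but promises no such model term; setting is affected only if it is fitted.

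The error rates rest on assumed ICCs and cluster sizes, and fall with fewer analysed per clinic. Finally, the plan points to a sample size section that is not in the available text, so it can be said only that no stratum is named in what can be read. The pairing of the branches does not depend on that section. The branches may have been swapped by accident in drafting; an analyst who follows the text would still apply the wrong model.

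**Conclusion.** The rule is wrong as written, and this does not depend on any assumed figure. It attaches the clinic and state random-effects model to the absence of clustering. In the clustered branch it leaves the ORCA main effect on binary outcomes either inestimable or, with wider strata and no clinic term, tested with about 8.5%, 32% or 62% true error at ICC 0.001, 0.01 or 0.05 and 292 per clinic (6%, 16% or 42% with 100). Those percentages are conditional on the assumptions above and are not a forecast for the trial. An ORCA category set by institution also drops out with institution strata, and the ordinal outcomes have no clustered-data method.

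The documents do not support the broader conclusion that the effectiveness analysis as a whole is invalid: patient-level associations and within-clinic change contrasts are sound with clinic strata. Because the harm is confined mainly to one promised explanatory variable and the missing ordinal method, this is a point that should be fixed, and not one that undermines the study.

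**What to change.** - Delete the design-effect trigger. Whatever the design effect, use the mixed model already named, in logistic or ordinal form, with clinic as a random intercept and state as a random effect.
- State that clinic and provider are controlled by random effects (provider nested in clinic) in any model that tests a clinic- or institution-level factor.
- For factors set by clinic, base degrees of freedom on the number of contributing clinics, less the terms fitted at that level.
- Categorise ORCA by clinic. If it is set by institution, add an institution random effect (state can serve only if the two coincide, which the documents do not say) and base both the standard error and the degrees of freedom on the five institutions.
- Conditional logistic regression may stay, with clinic as the named stratum, for patient-level factors and within-clinic contrasts.

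The cost is plan wording and standard software, with no new data. Intervals for clinic-level effects become wider, and honestly so. At ICC 0.01, a 30% outcome rate and 12 v 12 clinics, the standard error is √(2 × 0.3 × 0.7 × 3.91/(12 × 291.7)) = 0.0217. The smallest difference detectable with 80% power (noncentral t, 22 df) is then about 6.3 points, against 2.80 × √(2 × 0.3 × 0.7/(12 × 291.7)) = 3.1 points if clinic is ignored. An ORCA category set by institution has little power. With 2 v 3 institutions, 3 df and clinic ICC 0.01, it needs about 9.4, 15.7 or 20.1 points at institution ICC 0, 0.005 or 0.01, which is a further reason to set the category by clinic.

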Resulting outcomes data, including all referrals, diagnoses, laboratory and genetic test results, medical procedures, office and ER visits, hospitalizations and medications that occur will be abstracted from patient medical record files prior to patient enrollment and throughout the study period by the participating clinics after patient participation has been concluded at each site and provided to the Duke statistical analysis team with only the patient's unique ID number.

Selection of Subjects –

Population: Study subjects will be comprised of providers and patients at the diverse clinics within in each of the 5 organizations (Duke University, Medical College of Wisconsin, Essentia Health, University of North Texas Health Science Center, and the Air Force).

Providers: all providers in the participating clinics will be selected to be included in the study. We anticipate 100% participation, for an expected enrollment of 365 providers.

ORCA survey participants will be providers, nurses, and administrators at participating clinics at each institution which are involved in MeTree implementation.

Key informants will be providers, nurses, and schedulers at each participating clinic which is involved in MeTree implementation.

Patients: All adult English or Spanish speaking patients scheduled for non-acute visits within 2 weeks will be invited to enroll when they schedule an appointment with their physician. Since this proposal focuses upon prevention and not disease management strategies, those with a study disease (breast, or colon cancer, hereditary cancer syndromes, or CHD) will not be excluded from enrollment but will be excluded from analyses relevant to their disease. We anticipate enrolling 7000 participants at a minimum (to achieve significance for effectiveness measures), but as an observational study will continue to enroll as many as are interested in order to maximize our ability to assess differences across settings, populations, and sociodemographic factors. To reach this goal we need to enroll ~300 participants from each intervention clinic (assumes 10 of the 34 clinics will be dedicated controls). Assuming 20% enrollment (from MeTree™ pilot -see preliminary data), we anticipate being able to enroll at least 9,100 participants.

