Patient recruitment will be initiated with requests to participate mailed when a well visit appointment is made or a reminder sent from the scheduling service at each intervention study site. Each invitation will include all the elements of informed consent, including a description of the study, its risks and benefits, further information about the surveys and description of the electronic consent process. Those who are interested will contact the central Duke study coordinator who may briefly review the study again. If the patient is interested, the Duke study coordinator will provide the participant with a web-based computer survey program account where they will complete the enrollment and consent process.

If the invited patients do not respond within the expected time window prior to their scheduled appointment the local site coordinators may follow up with a phone call to provide additional information about the study and to encourage their participation. If during this phone call patients express interest in enrolling the site coordinator will advise them to call Duke central office directly or will offer to contact Duke on their behalf. If latter, local site coordinators will collect/verify the following information and will submit in a secure email to [contact]:

- a. name (first, middle if any, last)
- b. email address (this will be the participants login, and to which all emails will be sent)
- c. did they set up this email specifically to participate in this study?
- d. institution
- e. verification that the participant is 18 years of age or older
- f. phone number
- g. gender
- h. date of birth
- i. clinic name
- j. provider name
- k. appointment date
- l. preferred language (English / Spanish)
- m. Medical record number or local unique identifier

Upon receipt of this information Duke study coordinator will complete the registration and notify participant via email. The local site coordinator will monitor this process in the site specific census.

There will be no compensation to provider, other clinic personnel, or patient participants.

Consent Process:

Providers will be consented in person by local study staff at each participating Institution after they have been provided with onsite education (by the local study staff) about the study and as to why they would want to participate. Should they agree, they will sign the consent form and receive an electronic survey link via email.

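### Offering the intervention to everyone does not make effect-size bias extremely unlikely: enrolment is voluntary (assumed 20%), and the supplied text does not state the effectiveness contrast

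*Combined protocol and SAP*

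**What the plan says.** Under Data Analysis & Statistical Considerations the plan asserts that "Effect size bias is extremely unlikely in this study as all individuals within the clinics are offered the intervention". It credits the universal offer with "preventing the imbalance in treatment assignment that can lead to inaccurate point estimates". The same paragraph, arguing that clustering is improbable, notes that "all participants undergo the intervention".

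Selection of Subjects says that adult patients "scheduled for non-acute visits within 2 weeks will be invited to enroll". Its planning figure is "Assuming 20% enrollment", from which "we anticipate being able to enroll at least 9,100 participants". Under Subject Recruitment and Compensation, invitations go out from intervention sites. "Those who are interested will contact the central Duke study coordinator", and they then consent online.

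On controls, Purpose of the Study labels the design both cluster randomised and observational. It assumes that 10 of 34 clinics are controls, and the usual-care comparison it names is the cost-effectiveness analysis. Design & Procedures speaks of one randomly assigned comparator clinic, used to track changes in standard care. For the effectiveness outcomes, the analysis section has no arm term, no control population and no intervention-versus-control comparison. It refers to a sample size section for its seven covariates, and that section is not in the supplied text.

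**The concern.** The bias sentence treats being offered the intervention as if it were receiving it. Balance in the offer says nothing about balance in uptake, and uptake decides who contributes data: surveys go to consented participants, and record data are supplied under the patient's study ID.

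The study aims to produce evidence of clinical utility as well as to study adoption. A reader who relies on this sentence would take a favourable result as an unbiased intervention effect. The result could instead reflect change in care over time or, in a comparison with control clinics, who chose to enrol. The supplied text would not let the reader tell these apart.

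**Working it through.** **1. The plan's own figures.** With 10 of 34 clinics as controls, 34 − 10 = 24 intervention clinics. At about 300 each, 24 × 300 = 7,200, against the stated minimum of 7,000 (7,000/24 = 291.7 per clinic). The recruitment arithmetic therefore reproduces. The 9,100 cannot be checked, because the number approached is not given. If the 20% applies to those invited, which the text does not say outright, 9,100/0.20 = 45,500 are invited and 45,500 − 9,100 = 36,400 do not enrol.

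**2. Does the offer balance receipt?** The offer goes to eligible patients at intervention sites. Receipt follows the patient's decision to enrol, which about one in five is expected to make. All of those who enrol receive the intervention. The premise of the bias sentence concerns the offer, and its conclusion concerns the effect estimate; the one does not imply the other.

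**3. Which contrast could the sentence protect?** The text allows three readings.
- *Change over time within enrollees* (baseline, 3-month and 12-month surveys; records from before enrolment onward). The same people are compared with themselves, so self-selection mainly limits generalisability. Background trend and regression to the mean remain in the estimate.
- *Enrollees against control-clinic patients.* One group chose to take part and the other was never asked. Self-selection can bias this directly.
- *All eligible patients, intervention clinics against control clinics.* Randomising clinics would protect this one, but the supplied text does not specify it.

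Under neither contrast that uses enrollees does the offer make bias improbable.

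**4. What would reduce bias in an enrollee-versus-control comparison?** Let *f* be the enrolment fraction and *d* the gap in outcome between enrollees and decliners. Suppose there is no true effect, the clinics are otherwise alike, and the control group is all eligible control-clinic patients.
- Comparing levels at follow-up: bias = (1 − *f*) × *d*.
- Comparing changes: bias = (1 − *f*) × (*d* after − *d* before). This is zero only if the gap stays constant.
- Adjusting for the baseline value, with a constant gap and within-group slope *b* of follow-up on baseline: bias = (1 − *f*) × *d* × (1 − *b*). Unless *d* is zero, this is zero only if *b* = 1.

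Change and baseline adjustment are therefore not interchangeable here. The documents give no *d*, no shift in *d* and no *b*, so no bias figure is computed.

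**5. Number of control clinics.** Design & Procedures gives one. Read as one per institution, it gives five. Purpose of the Study and Selection of Subjects give 10. The target of about 300 per clinic fits 10 controls; with five it would be 7,000/29 = 241.4.

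**The case against.** The strongest reply is that the supplied models look like analyses within enrollees. They control for clinic and provider, the surveys are repeated in participants, and all participants are treated. Self-selection is then chiefly a question of generalisability. This stands, and it changes the main threat to trend and regression to the mean. It does not rescue the sentence, which gives no reason to exclude either.

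A second reply is that the sample size section and the preliminary data cited in the plan are not supplied and may state the contrast. This also stands. A reader might infer that no effectiveness contrast was ever defined, but the documents do not support that. The missing contrast is a query.

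Third, the plan calls itself observational and makes reach and adoption outcomes, so selective uptake is partly what it studies. That is fair context, but it is a reason to drop the assurance about effect size.

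Three further inferences should be resisted.
- A reader might conclude that the results will be inflated, or put a number on it. Nothing in the documents gives a direction or size.
- A reader might credit the plan with adjusting for demographics and intent to change. These enter only if stepwise selection at p < 0.1 retains them.
- A reader might see a contradiction between voluntary provider participation and the expected 100%. A voluntary choice can still be expected to be unanimous.

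**Conclusion.** The sentence is wrong as written and should be withdrawn. Universal offer does not prevent imbalance in receipt when enrolment is voluntary and assumed to be 20%. Which bias matters depends on the contrast: trend and regression to the mean within enrollees, or self-selection against control-clinic patients. The size and direction cannot be derived from the documents.

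The finding about the sentence rests only on the plan's own text. The finding that the effectiveness contrast is unstated is limited to the supplied text and goes to the sponsor as a question. The conflict over the number of control clinics is real on either reading of Design & Procedures. This should be fixed; confidence is moderate.

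**What to change.** 1. Replace the bias sentence with: *Patients choose whether to enrol (assumed 20%). Offering the intervention does not balance who receives it; comparisons of enrollees with control-clinic patients are non-randomised, and enrollee-only changes are uncontrolled.* Ask the sponsor which contrast the effectiveness models estimate, and state it in the analysis section.
2. Report any effectiveness result estimated in enrollees only as an uncontrolled before-after change, not as an unbiased intervention effect. This includes the 3- and 12-month surveys if no control data exist.
3. If enrollees are compared with control-clinic patients, including for the effect input to the cost-effectiveness analysis, and control records are available, select controls by the same non-acute-visit rule and calendar period. Estimate the group-by-period difference in change; for binary outcomes, use a group-by-period term in the logistic mixed model. State that this assumes a constant enrollee-decliner gap on the model's scale and does not remove unmeasured motivation.
4. Separately, reconcile the number of control clinics between Design & Procedures and the other two sections.

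Items 1, 2 and 4 are wording. Item 3 costs some control-record abstraction, which the supplied text does not describe, and any consent or waiver it needs. Pre-enrolment records are already to be abstracted for participants. A comparison of all eligible patients by clinic is not requested: at 20% uptake, and with no effect in non-enrollees, it would show only 0.20 of the effect in enrollees.
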